3.1.2 Study day

Whenever data is summarised over time, study day will be calculated based on the actual assessment date. Efficacy data assessments will be summarised in relation to date of randomisation. Safety data will be summarised in relation to date of first dose.

If actual assessment date is prior to randomisation / first dose then study day will be:

$$\text{Study day} = \text{Actual assessment date} - \text{Randomisation / first dose date.}$$

If actual assessment date is on or after randomisation / first dose then study day will be:

$$\text{Study day} = \text{Actual assessment date} - \text{Randomisation / first dose date} + 1.$$

3.1.3 Absolute and percent change from baseline

Absolute change from baseline outcome variables is computed as

(post-randomisation value – baseline value).

Percent change from baseline is computed as

((post-randomisation value – baseline value) / baseline value) × 100%.

If either the post-randomisation value or the baseline value is missing, then the absolute or percent change from baseline value will also be set to missing.

Percentage change from baseline will not be calculated or presented for variables that may take 0 as a value.

3.1.4 Visit windows

For the exacerbation-related analyses no windows will be applied.

Daily eDiary and ePRO data (PEF, ACQ-5, FeNO) will primarily be summarised and analysed as weekly averages e.g. over days 2 - 8, 9 - 15 and 16 - 22 etc, separately. The assessment period of visit windows will be defined in Appendix A, [Table 5](#).

Summaries and analyses of non-eDiary or non-ePRO data will be based on CRF visit designation, defined in Appendix A, [Table 6](#).

Any data collected at unscheduled visits will be listed, included within baseline data in shift plots, and will be included in the definition of maximum/minimum within-period value.

The Unscheduled visits will be included when applying the visit windows to ensure that all available data are used in the analysis. For weekly summaries, the mean of all non-missing observations within an assigned window is calculated. For visit data, if there are duplicate observations assigned to the same visit window, the following data handling conventions will be adopted:

1. If there are two or more observations within the same visit window, the non-missing observation closest to the scheduled visit will be used in the analysis.
2. If two observations are collected on the same day, the non-missing observation with the later collection time will be included in the analysis.

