5.3.2 Sputum induction

Sputum induction should be performed in a subgroup of patients (approximately 20% of the patients) at selected sites according to local procedures. An FEV1 measurement will be performed after the each sputum induction cycle for safety reasons.

The method for processing of induced sputum will be described in the Laboratory Manual. The sputum collection is also summarized in Section 5.5.1.

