3. PRIMARY AND SECONDARY VARIABLES

3.1 General Principles

3.1.1 Baseline definitions

In general, the last measurement on or prior to the date of randomisation will serve as the baseline measurement for efficacy endpoints, while the last measurement prior to first dose of IP will serve as the baseline measurement for safety endpoints.

For the following parameters, only measurements recorded at the baseline visit (Visit 2 (Week 0)) taken pre-bronchodilator are considered for the baseline: Inspiratory Capacity (IC), FEV₁/FVC ratio, FEV₁ reversibility, FEV₁ reversibility (%), Diffusing Capacity of the Lung Carbon Monoxide (DLco), FeNO, average FeNO.

If Visit 2 (Week 0) measurement is missing, the last non-missing value before Visit 2 will be used as baseline instead.

For the following parameters, baseline is calculated at each timepoint (pre-bronchodilator and post-bronchodilator): FEV₁, Forced Vital Capacity (FVC), Forced Expiratory Flow 25%, Forced Expiratory Flow 75%, Forced Expiratory Flow 25% to 75% (FEF25-75%) and PEF (collected at the clinic). For post-bronchodilator (BD) measurements, where it is possible to have multiple spirometry records per time point, the first measurement will be used (i.e. the measurement after the first BD administration).

The baseline for Electronic Patient Reported Outcome (ePRO) will be derived from what is captured on the ePRO device 5 days prior to Visit 2 (Week 0) for PEF, Asthma Daily Diary scores and Reliever medication use. The 5 days do not have to be strictly consecutive.

For night-time baseline diary scores, the calculations should comprise 5 mornings including the morning of randomisation. For daytime baseline diary scores, the calculations should comprise 5 evenings prior to randomisation.

For PEF evening baseline mean, the calculations should comprise of the mean of last 5 evening values prior to randomisation. For PEF morning baseline mean, the calculations should comprise of the mean of last 5 morning values prior to and including day of randomisation. For PEF baseline mean, this is calculated as the average of the morning baseline mean and the evening baseline mean.

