3.3.7 FEV₁ pre/post BD

The pre/post BD FEV₁ will be determined by the spirometry tests at the clinic at each visit as scheduled. To ensure quality control all spirometry measurements are reviewed to ensure that they meet ATS/ERS (American Thoracic Society 2000) criteria for acceptability. Section 5.1.2 of the CSP contains further details of the spirometry recordings.

The endpoints are:

- 1) absolute change from baseline in pre-BD FEV₁ (L)
- 2) percentage change from baseline in pre-BD FEV₁
- 3) absolute change from baseline in post-BD FEV₁ (L)
- 4) percentage change from baseline in post-BD FEV₁

The absolute changes from baseline are the main FEV₁ endpoints. The percentage changes from baseline are supportive endpoints.

A reversibility test will be performed at Visit 1 (Week -4), with spirometry assessment 30±10 minutes before and after administration of short-acting β₂ agonist.

The percent reversibility is calculated as follows:

Reversibility (%) = (FEV₁ post – FEV₁ pre) / FEV₁ pre x 100

The value of Percent predicted normal for FEV₁ used as part of the eligibility process will not be checked programmatically.

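### SAP 3.1.1 takes the first post-bronchodilator record but says so only under baseline, while SAP 3.1.4 takes the later same-day record for visit data; the two rules are not reconciled for change in post-BD FEV1

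*SAP*

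**What the plan says.** SAP 3.1.1 (Baseline definitions) states that for FEV1, FVC, the FEF measures and clinic PEF, "baseline is calculated at each timepoint (pre-bronchodilator and post-bronchodilator"). It foresees that after bronchodilator "it is possible to have multiple spirometry records per time point", and for that case it says that "the first measurement will be used (i.e. the measurement after the first BD administration").

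SAP 3.1.4 (Visit windows) deals with duplicates after baseline: "For visit data, if there are duplicate observations assigned to the same visit window, the following data handling conventions will be adopted". Rule 1 takes the non-missing observation nearest the scheduled visit. Rule 2 reads: "If two observations are collected on the same day, the non-missing observation with the later collection time will be included in the analysis". Neither rule excludes spirometry.

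SAP 3.3.7 lists "absolute change from baseline in post-BD" FEV1 among its endpoints. It calls the absolute changes the main FEV1 endpoints and the percentage changes supportive. SAP 3.1.3 defines the change as the post-randomisation value minus the baseline value. SAP 4.2.4.5 models FEV1 itself with the matching pre-BD or post-BD baseline as covariate, and adds descriptive summaries of change by arm and visit. Neither 3.3.7 nor 4.2.4.5 says which record to use when a later visit has several post-BD records.

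**The concern.** A change from baseline is interpretable only if both terms are measured in the same way. The first post-BD record follows one bronchodilator administration. A later record on the same day may follow more than one. If baseline takes the first and a later visit takes the later, part of the computed change can come from extra bronchodilator and not from treatment or disease.

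At stake are the by-visit summaries of change in post-BD FEV1 in each arm, the same summaries for post-BD FVC and FEF measures, and under some conditions the post-BD FEV1 treatment comparison. Even if no mismatch was intended, two programmers could follow the SAP in good faith and derive different visit values.

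**Working it through.** **Step 1: trace the two rules.** The plan has no figure of its own to reproduce here, because the issue is a derivation rule.

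- Baseline, several post-BD records: 3.1.1 gives the first.
- Later visit, several post-BD records on one day: 3.1.1 is silent if read as baseline-only. Under 3.1.4, rule 1 cannot separate the records because they are equally far from the target day, so rule 2 decides and gives the later.
- Change (3.1.3) = later-record visit value minus first-record baseline.

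If the 3.1.1 sentence is instead read as covering post-BD records at every visit, it gives the first and rule 2 gives the later for the same data. No order of precedence is stated.

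**Step 2: scale within an arm.** Let q be the share of patients with more than one same-day post-BD record at a visit, and x the last-minus-first difference in litres. The documents give neither, so both are assumptions. The shift in mean change is q × x (litres):

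| q | x = 0.03 | x = 0.05 | x = 0.10 | x = 0.15 |
|---|---|---|---|---|
| 0% | 0 | 0 | 0 | 0 |
| 10% | 0.003 | 0.005 | 0.010 | 0.015 |
| 30% | 0.009 | 0.015 | 0.030 | 0.045 |
| 50% | 0.015 | 0.025 | 0.050 | 0.075 |
| 100% | 0.030 | 0.050 | 0.100 | 0.150 |

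**Step 3: scale between arms.** The bias in active minus placebo is (qA − qP) × x (litres):

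| qA vs qP | x = 0.03 | x = 0.05 | x = 0.10 | x = 0.15 |
|---|---|---|---|---|
| 30% vs 30% | 0 | 0 | 0 | 0 |
| 20% vs 40% | −0.006 | −0.010 | −0.020 | −0.030 |
| 10% vs 50% | −0.012 | −0.020 | −0.040 | −0.060 |

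**Step 4: check against a baseline-adjusted model.** A large simulation at one visit (400,000 patients, no true effect, x = 0.10 L, FEV1 regressed on treatment and baseline) gave these treatment differences:

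- no repeats: −0.0002 L
- 30% repeats in both arms: −0.0007 L, while mean change rose by 0.030 to 0.031 L in each arm
- 20% active vs 40% placebo: −0.0205 L, against −0.020 L from the formula

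So an equal repeat rate shifts the within-arm summaries and leaves the adjusted difference essentially unbiased. Bias needs unequal rates.

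**Step 5: after the fix.** If the same record is used at every visit, the discrepancy x is 0, and so are both the shift and the bias. No sample size, power or alpha figure changes.

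**The case against.** The strongest reply is that the SAP nowhere says a later visit takes the last post-BD reading. The 3.1.1 sentence is worded for post-BD measurements in general, and a specific spirometry rule would normally override a general duplicate rule. Rule 2 directly follows the statement that unscheduled visits enter the windows, which suggests that it was written for them. Applied blindly to all same-day FEV1, it would even choose post-BD over pre-BD, so it must work within a time point, where 3.1.1 already offers a rule. This may well be the intention, but it is not written: the sentence sits under baseline, and 3.1.4 claims all visit data without exception.

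It is also fair that repeat bronchodilator after baseline is not shown. SAP 3.3.7 places the reversibility test at Visit 1, Protocol 4.1 puts any re-test on a later calendar day, and no readable text describes repeat dosing at later visits. The schedule of events could not be read in full in the text reviewed. The serial sentinel readings are no source, since SAP 4.2.4.12 excludes them. This stands, and it means that the effect may be zero.

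Three stronger readings are tempting and are not supported:

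- **The rule hides drug effect.** A reader might infer that worse control on placebo brings more repeats. No document links repeats to control or arm. Patients who lose control resume ICS + LABA and are followed for only four more weeks (Protocol 4.3), which limits visits with uncontrolled obstruction.
- **Rule 2 selects readings taken after sputum induction.** Protocol 5.3.2 says: "An FEV1 measurement will be performed after the each sputum induction cycle for safety reasons". But on dosing days sputum is collected 24 hours after the dose (Protocol 5.5.1), and SAP 4.2.4.5 analyses pre-dose values. Only non-dosing visits stay open, and only if such readings were stored as visit spirometry, which nothing states.
- **Pre-BD selection needs the same change.** The general baseline in 3.1.1 is the last measurement on or before randomisation, and rule 2 takes the later value. Those are broadly consistent, and moving pre-BD visits to the first reading could create a new mismatch.

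**Conclusion.** The point holds as an unreconciled pair of rules. Read literally, they give a first-record baseline and a later-record visit value wherever a post-baseline visit has more than one same-day post-BD record. Read generously, they contradict each other with no stated precedence. Either way the SAP does not fix the derivation of one of its main FEV1 endpoints.

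The size is unknown. It is zero if no repeats exist after baseline. Across the assumed range (q from 10% to 100%, x from 0.03 to 0.15 L), within-arm mean change would be shifted upward by 0.003 to 0.15 L. An upward shift further assumes that the later record follows more bronchodilator and is higher. The adjusted treatment difference is biased only if repeat rates differ by arm, and the documents establish neither a difference nor its direction. This is a secondary endpoint, and time to loss of asthma control is unaffected. The finding merits a correction before unblinding, not a claim of demonstrated bias.

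**What to change.** Add to SAP 3.1.4 or 3.3.7: for post-BD spirometry (FEV1, FVC and the FEF measures), the record after the first BD administration is used at baseline and at every later visit, and rule 2 of 3.1.4 does not apply to repeated post-BD records. This extends the sponsor's own baseline rule to all visits. The same wording can cover clinic PEF, which 3.1.1 lists in the same paragraph. Leave pre-BD selection as it is.

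The cost is one sentence and a change to the record-selection flag in the spirometry analysis dataset. No new data are needed. A blinded count of visits with more than one same-day post-BD record would show whether the point has any practical effect.

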3.1.5 Handling of missing data

All efficacy analyses will be based on the Full Analysis Set. Missing data rules for efficacy endpoints can be found in Sections 3.2 and 3.3. For eDiary endpoints (derived datasets ADQS, ADRE, ADEXSUM), when weekly means are calculated for summary statistics this will be calculated as the average of the non-missing values over a period of 7 sequential days e.g. if non-missing values are only recorded for 3 days then the denominator for the mean is 3. For

rescue medication weekly mean calculation where a patient discontinues treatment part-way through a week, the mean would be calculated as the average of what is recorded regardless of how many days were recorded in that part-week. For the eDiary endpoint rescue medication, in the event that a patient has recorded that they have taken rescue medication (ASMDMQ2=1) but the associated number of puffs collected is missing or recorded as zero (ASMDMQ2A=missing or 0), this missing or zero value will be changed to EXDOSE=1 in the SDTM datasets,

As the daily total for Asthma Daily Diary scores and Reliever medication are defined as the sum of the daytime and night-time scores on a specific day (e.g. sum of day 1 evening plus day 2 morning), if either daytime or night-time scores is missing, the daily total is set to missing.

Missing safety data will not be imputed.

Laboratory values of the form “<x” (i.e. below the lower limit of quantification) or “>x” (i.e. above the upper limit of quantification) will be imputed as “x” in the calculation of summary statistics but displayed as “<x” or “>x” in the listings.

For the diagnosis of Allergic Rhinitis, age at asthma diagnosis, years since most recent exacerbation and similar variables based on date calculations, if only partial dates are recorded, these will be imputed as the earliest possible date e.g. if day is missing but month and year are present then the 1st of the month will be imputed in order to derive the time since diagnosis variable. If the day and month are missing but the year is present, then the 1st January of that year will be imputed in order to derive the time since diagnosis variable. Partial dates will be flagged in listings and the analysis.

3.2 Primary efficacy outcome measure

The primary outcome measure is time to loss of asthma control. The EXACA module of the eCRF will be used to derive the Loss of asthma control variable. For the purpose of the study, loss of asthma control is defined as any of the following:

a) An increase of ACQ-5 to 1.5 or more

In the ACQ-5 questionnaire the patients are asked to recall the status of their asthma during the previous week with regards to symptoms. The questionnaire include questions on

1. Awoken at night by symptoms
2. Limitation of normal daily activities
3. Waking in the morning with symptoms
4. Dyspnoea
5. Wheeze

The questions of the ACQ-5 will be measured on a 7-point scale scored from 0 (totally controlled) to 6 (severely uncontrolled). The ACQ-5 score is computed as the un-weighted mean of the responses. If response to any of the questions is missing, the ACQ-5 score is set to missing by the ePRO provider. If ACQ-5 reaches a value of 1.5 or more, the patient is reported as having loss of asthma control.

- b) A reduction of 30% or more in morning peak expiratory flow (PEF) from baseline on 2 consecutive days

PEF is measured daily using the ePRO device. Patients should perform 3 successive peak flow manoeuvres while sitting or standing, but in the same position at every testing; the highest of the 3 values will be captured for the morning and for the evening manoeuvres.

- c) At least six additional reliever inhalations of SABA in a 24-hour period relative to baseline on 2 consecutive days

The number of reliever medication inhalations taken will be recorded by the patient in the Asthma Daily Diary twice daily. The number taken between the morning and evening lung function assessments will be recorded in the evening. The number of inhalations taken between the evening and morning lung function assessments will be recorded in the morning. Reliever medication usage is captured in the daily diary as the number of inhaler puffs.

- d) An exacerbation requiring systemic corticosteroids

Upon a), b) or c) being fulfilled, an automated asthma action plan will be triggered in the ePRO device prompting the patient to resume their usual ICS + LABA medication and to contact the PI.

The primary endpoint Time to loss of asthma control will be calculated as follows:

$$\text{Start Date of first loss of asthma control} - \text{Date of Randomisation} + 1.$$

The start date of the first loss of asthma control will be the earliest of:

1. Date of the first increase in ACQ-5 of 1.5 or more
2. Date of the first of two consecutive days with a reduction of 30% or more in PEF
3. Date of the first of two consecutive days with six additional SABA inhalations relative to baseline
4. Date of the earliest use of systemic corticosteroids to treat an asthma exacerbation

Time to loss of asthma control will be censored at 52 weeks for patients who do not experience loss of asthma control during the 52-week study period or at the time point after which an loss of asthma control experience could not be assessed (for lost-to-follow-up patients). For patients who withdraw from the study without reporting loss of asthma control, time will be censored at the date of withdrawal, if known, else at the patient's last clinical visit plus one day.

3.3 Secondary endpoints

Secondary efficacy variables include proportion of patients with loss of asthma control, ACQ-5, eDiary variables, proportion of patients with a moderate or severe exacerbation, PEF, FEV₁ and FeNO. These are described in more detail below.

3.3.1 Proportion of patients who experience loss of asthma control

The proportion of patients who experience loss of asthma control during the 52-weeks of treatment will be a supportive measurement to the primary objective. The outcome variable will categorize each patient as having loss of asthma control symptom being met or not (yes=1/no=0).

The proportion of such patients will be calculated for each treatment group as:

Number of patients with loss of asthma control indication during the 52-week treatment period/ number of patients in treatment group

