8.2 Sample size estimate

This trial has about 90% power to yield a statistically significant ($\alpha = 0.05$, 2-sided) difference between the pooled active and placebo groups in time to loss of asthma control given that the cumulative number of controlled subjects at week 52 is 20% and 60% for control versus active respectively. Assuming a drop-out of about 10-15%, this will require about 70 patients in total (32 events).

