8.5.4 Analysis of the primary variable (s)

The primary efficacy variable is the time to loss of asthma control, and the primary analysis is to compare the time to loss of asthma control for AZD1419 with placebo. The Time to loss of control in the AZD1419 group will be compared to that of the placebo group using a log rank test (with accompanying Kaplan-Meier plot)

The hypothesis test will be one-sided, with $\alpha=0.05$.

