1.3 Number of patients

This trial has about 90% power to yield a statistically significant ($\alpha = 0.05$, 2-sided) difference between the pooled active and placebo groups in time to loss of asthma control given that the cumulative number of controlled patients at week 52 is 20% and 60% for control versus active respectively. Assuming a drop-out of about 10-15%, this will require about 70 patients in total (32 events).

Approximately 135 patients have been enrolled to achieve 81 randomised patients.

Figure 1
Study flow
chart

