5.1 Sensitivity analysis

An analysis will be conducted on the primary outcome variable, loss of asthma control, using the same log rank test as for the primary analysis, but making the assumption that all patients who withdraw from the study without recorded loss of control are classed as loss of control (instead of being censored), in order to test the sensitivity of the results to the use of censoring/lack of information regarding loss of control in patients who withdraw.

Summary statistics will be produced for the reliever medication for each treatment group over time for the weekly average and the change from baseline in weekly average by 1) imputing missing values to zero and 2) imputing using last observation carried forward (LOCF) method.

Summary statistics will be produced for Asthma Symptom scores (weekly total: mean total daily score, number of asthma symptom free days and proportion of asthma symptom free days endpoints) for each treatment group over time for the weekly average by 1) imputing missing values to zero and 2) imputing using last observation carried forward (LOCF) method.

For LOCF, the missing values will be populated until the patient has their next non-missing value or until the patient either completes the study or withdraws from the study. For both imputation methods, the individual missing values should be imputed (not daily sums or weekly averages).

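### SAP 3.3.1 scores event-free withdrawals as no loss of control, so the 52-week proportion is understated, and unequal withdrawal would favour the arm with more of it

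*SAP*

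**What the plan says.** SAP 3.3.1 codes each patient 1 or 0 for loss of control and defines the proportion per arm as "Number of patients with loss of asthma control indication during the 52-week treatment period/ number of patients in treatment group". It calls the measure supportive of the primary objective. SAP 1.1.2 lists it first among the secondary outcomes. Efficacy analyses use the full analysis set, which SAP 2.1.2 limits to randomised patients who received IP.

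The plan handles event-free withdrawal in two other places:

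- **Primary variable (SAP 3.2):** "time will be censored at the date of withdrawal, if known", otherwise one day after the last clinic visit.
- **Sensitivity analysis (SAP 5.1):** "all patients who withdraw from the study without recorded loss of control are classed as loss of control". This is specified for the log-rank test only.

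SAP 4.2.4 plans a Kaplan-Meier plot of the primary variable, and SAP 6 mentions added summary statistics for it. Neither names an estimate at Week 52 with a confidence interval. The between-arm comparison of the proportion, in SAP 4.2.4.1, is a per-visit model, not a test of the 3.3.1 ratio.

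**The concern.** Under the 3.3.1 rule, a patient who leaves event-free at Week 5 gets the same score as one observed in control for 52 weeks. Protocol 4.2 withdraws LABA just before dose 7 and ICS just before dose 10, so the Week 5 patient has not yet begun the taper. Each such patient lowers the arm's reported loss of control.

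Readers will naturally set this percentage against the design assumption in SAP 1.3, "cumulative number of controlled patients at week 52 is 20% and 60% for control versus active respectively". If the arms differ in event-free withdrawal, the percentages will also differ for a reason unrelated to efficacy. Protocol 4.2.2 describes one route that could be unequal: patients who cannot tolerate the 1 mg dose stop dosing and leave the study after four more weeks.

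**Working it through.** **Inputs.** Controlled at Week 52: 20% placebo, 60% active (Protocol 8.2, SAP 1.3), so loss of control is 80% and 40%. Drop-out is 10-15% overall (same sections). Drop-out by arm is not given, so unequal rates below are assumptions.

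**The plan's own figure.** Protocol 8.2: "Assuming a drop-out of about 10-15%, this will require about 70 patients in total (32 events".
- Hazard ratio = ln 0.6 / ln 0.2 = 0.317.
- Events (Schoenfeld, two-sided 0.05, 90% power) = 4 × (1.960 + 1.282)² / (ln 0.317)² = 31.9, so 32. This reproduces.
- A two-proportion calculation (80% v 40%) gives 30 per arm, 60 in total. 60/0.90 = 67 and 60/0.85 = 71, consistent with about 70. The documents do not say which route was used.

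**Model A: withdrawal times uniform over 0-52 weeks for a fraction d of all patients.** Hazard is zero to Week 9, then constant. With S the proportion controlled at Week 52:
- h = −ln S / 43
- mean F = [43 − (1 − S)/h] / 52, the average cumulative loss at a random withdrawal time. This is 0.416 for S = 0.2 and 0.179 for S = 0.6.
- Crude proportion = (1 − d)(1 − S) + d × mean F

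**Model B: d is entirely event-free withdrawal.** Event rate λ and independent withdrawal rate μ are constant, with 52 weeks as the time unit:
- P(event) = λ[1 − e^−(λ+μ)] / (λ+μ), where λ = 1.609 (placebo) or 0.511 (active)
- μ is chosen so that μ[1 − e^−(λ+μ)] / (λ+μ) equals the stated withdrawal. For 10%, μ = 0.218 (placebo) and 0.136 (active).

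**Equal withdrawal, true loss 80% v 40%**

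| Withdrawal | Model | Placebo | Active | Difference |
|---|---|---|---|---|
| none | either | 80.0% | 40.0% | 40.0 |
| 10% | A | 76.2% | 37.8% | 38.4 |
| 15% | A | 74.2% | 36.7% | 37.5 |
| 10% | B | 73.9% | 37.6% | 36.3 |
| 15% | B | 70.8% | 36.4% | 34.4 |

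Example (A, 15%, placebo): 0.85 × 0.80 + 0.15 × 0.416 = 0.742. Model A gives the smaller bias because some of its withdrawal times fall after an event: of the 15%, only 0.15 × (1 − 0.416) = 8.8% withdraw event-free on placebo.

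**Unequal withdrawal (assumed), true loss 80% in both arms, 5% placebo v 20% active**
- A: 0.95 × 0.80 + 0.05 × 0.416 = 78.1%; 0.80 × 0.80 + 0.20 × 0.416 = 72.3%. False advantage 5.8 points.
- B: 77.0% v 67.6%. False advantage 9.4 points.
- Reversing the rates gives the same size against AZD1419. With true loss of 60% in both arms, B gives 6.1 points.

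**Alternatives in the same settings.** Kaplan-Meier with non-informative withdrawal targets the true values: 80% v 40%, or 80% v 80%. Counting withdrawal as loss (B) gives 83.9% v 47.6% at 10% and 85.8% v 51.4% at 15%. In the unequal null case it gives 82.0% placebo v 87.6% active, an error of 5.6 points the other way.

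**The case against.** The strongest reply is that the ratio is a crude observed incidence: it records whether the criterion was seen, and makes no claim that a withdrawn patient stayed in control. A Kaplan-Meier plot with censoring is already planned, and its Week 52 height is the better estimate. Disposition tables and a plot of time to study withdrawal (SAP 4.2.1) would reveal any imbalance. No test uses the 3.3.1 ratio.

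Much of this stands. A reader might infer that no planned output estimates Week 52 control without this bias; the planned plot contradicts that. A reader might also see an inconsistency between censoring in the primary analysis and withdrawal as loss in SAP 5.1. That contrast is deliberate, since SAP 5.1 exists to test the effect of censoring. Whether the ratio conflicts with the no-imputation statement in Protocol 8.1 is a matter of interpretation, and the point does not depend on it.

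The formula itself is not answered. Followed as written, it reports a 52-week proportion that falls as event-free withdrawal rises. The plotted curve comes with no specified Week 52 figure or interval, and the 5.1 analysis does not reach this endpoint.

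**Conclusion.** The point holds for the descriptive proportion in SAP 3.3.1. At the plan's own drop-out, loss of control is understated by about 4-9 points on placebo (80% to 71-76%) and 2-4 on active (40% to 36-38%), and the difference shrinks from 40 to about 34-38 points. These figures assume withdrawal independent of asthma risk. If patients who withdraw are at higher risk, the understatement is larger.

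Stronger readings are not supported:
- The denominator is the treated full analysis set, not everyone randomised.
- Only event-free withdrawals are affected. A patient with a recorded loss of control scores 1 whatever happens later.
- The formula does not favour AZD1419 in itself. With equal withdrawal it dilutes the effect. The 6-9 point false advantage needs unequal withdrawal, and the 5% v 20% split is an assumption. Intolerance could plausibly be more common on active, but dose adaptation (Protocol 4.2.2) narrows that route, and stopping IP is not by itself leaving the study (SAP 4.2.1).
- The primary log-rank test is unaffected, and no bias has been shown here for the per-visit model in SAP 4.2.4.1.

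**What to change.** In SAP 3.3.1, define the 52-week proportion with loss of control as the Kaplan-Meier estimate at Week 52 in each arm, with 95% CI and the between-arm difference with its CI, from the PROC LIFETEST run planned in SAP 4.2.4. Report crude counts per arm in three categories: lost control, controlled at Week 52, withdrawn event-free. Extend SAP 5.1 so that this proportion is repeated with withdrawal counted as loss.

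The cost is a few lines of SAP text and slightly more output, with no new data. Kaplan-Meier assumes non-informative withdrawal, so the repeat is needed alongside it.
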